14.2 Examples of light meal

Example 1:	amount	kcal	g total fats
Wheat Bread or Toast	2 slices	138	2
jams, preserves, all flavors	1 Tablespoon	109	0
banana	medium (7-7 7/8" long)	105	0
orange juice	1 cup	114	0
skim milk	1 cup	83	0
Total:		549	2

Example 2:	amount	kcal	g total fats
Pita Bread	1 medium (5.25" across) pita	124	1
hummus or deli chicken/turkey	1 Tablespoon humuus or 2 oz meat	27	1
apple	medium (2.75" across)	72	0
salsa, red, cooked	6 Tablespoons	26	0
carrots & celery sticks	4 carrot sticks (3" long) and small 5" stalk of celery	14	0
Total:		263-295	2

Example 3:	amount	kcal	g total fats
yogurt, fruit, low-fat	6 oz	173	2
banana	medium (7-7 7/8" long)	105	0
orange juice	1 cup	114	0
skim milk	1 cup	83	0
Total:		475	2

Example 4:	amount	kcal	g total fats
vegetable chicken noodle soup, canned	1 cup	70	2
baked potato, peel not eaten	1 medium (2.25-3" across)	121	0
skim milk	1 cup	83	0
banana	medium (7-7 7/8" long)	105	0
Total:		379	2

Example 5:	amount	kcal	g total fats
egg whites, cooked, no fat added	2 large egg whites	32	0
salsa, red, cooked	6 Tablespoons	26	0
Wheat Bread or Toast	2 slices	138	2
jams, preserves, all flavors	1 Tablespoon	109	0
orange juice	1 cup	114	0

skim milk	1 cup	83	0
	Total:	502	2

Example 6:

chicken, boneless, skinless baked	0.5 cup diced	111	2
salsa, red, cooked	6 Tablespoons	26	0
white rice, cooked, no fat added	0.5 cup	102	0
black beans, canned or cooked from dry, no fat added	0.5 cup	99	0
skim milk	1 cup	83	0
	Total:	421	2

14.3 Algorithm for Preference questionnaire completion

In case of treatment switch during the Core Phase of the study, the investigator must provide the preference questionnaire to the patient in the immediate next visit and then keep following the schedule of questionnaires pre-planned on [Table 7-1](#) and [Table 7-2](#).

Please see below the preference questionnaire version to be completed, based on treatment switch (yes/no) and when it occurred.

- Scenario 1 – Patient does NOT switch treatment

STUDY VISIT	QUESTIONNAIRE VERSION
Visit 4 (week 4)	Questionnaire vs. week 4 and 24
Visit 9 (week 24)	Questionnaire vs. week 4 and 24
Visit 10 (week 28)	Questionnaire vs. week 28
Visit 15 (week 48)	Questionnaire vs. week 48

- Scenario 2 – **Treatment switch** happens V3

STUDY VISIT	QUESTIONNAIRE VERSION
Visit 4 (week 4)	Questionnaire vs. week 28
Visit 9 (week 24)	Questionnaire vs. week 28
Visit 10 (week 28)	Questionnaire vs. week 28
Visit 15 (week 48)	Questionnaire vs. week 48

- Scenario 3 – Treatment switch happens between Visit 4 to Visit 7

STUDY VISIT	QUESTIONNAIRE VERSION
Visit 4 (week 4)	Questionnaire vs. week 4 and 24
Unplanned – next study visit after treatment switch	Questionnaire vs. week 28 eCRF: Summary page -
Visit 9 (week 24)	Questionnaire vs. week 28
Visit 10 (week 28)	Questionnaire vs. week 28
Visit 15 (week 48)	Questionnaire vs. week 48

- Scenario 4 – **Treatment switch** happens at **visit 8**

STUDY VISIT	QUESTIONNAIRE VERSION
Visit 4 (week 4)	Questionnaire vs. week 4 and 24
Visit 9 (week 24)	Questionnaire vs. week 28
Visit 10 (week 28)	Questionnaire vs. week 28
Visit 15 (week 48)	Questionnaire vs. week 48

- Scenario 5 – **Treatment switch** happens at **visit 9**

STUDY VISIT	QUESTIONNAIRE VERSION
Visit 4 (week 4)	Questionnaire vs. week 4 and 24
Visit 9 (week 24)	Questionnaire vs. week 4 and 24
Visit 10 (week 28)	Questionnaire vs. week 28
Visit 15 (week 48)	Questionnaire vs. week 48

- Scenario 6 – **Treatment switch** happens at visit 10 to 13

STUDY VISIT	QUESTIONNAIRE VERSION
Visit 4 (week 4)	Questionnaire vs. week 4 and 24
Visit 9 (week 24)	Questionnaire vs. week 4 and 24
Visit 10 (week 28)	Questionnaire vs. week 28
Unplanned – next study visit after treatment switch	Questionnaire vs. week 48 eCRF: Summary page -
Visit 15 (week 48)	Questionnaire vs. week 48

- Scenario 7 – **Treatment switch** happens at **visit 14**

STUDY VISIT	QUESTIONNAIRE VERSION
Visit 4 (week 4)	Questionnaire vs. week 4 and 24
Visit 9 (week 24)	Questionnaire vs. week 4 and 24
Visit 10 (week 28)	Questionnaire vs. week 28
Visit 15 (week 48)	Questionnaire vs. week 48

**Document History – Changes compared to previous final version of SAP**

| Date         | Time point            | Reason for update                | Outcome for update   | Section and title impacted (Current)  |
|---------------------|------------------------------|---|---|--|
| 03-
May-
2017 | Prior
to
DB
lock    | Creation of
final
version         | N/A - First version   | NA   |
| 10-
Jun-
2020 | Prior
to
DB
lock    | Creation of
Amendment
version 1.0 | Protocol amended. Modification in objectives and some definitions. Sample size calculation changed. DRP updated.  | Section 1.2,
Section 3,
appendix and
some parts of
other sections as
per modified
protocol |
| 04-
Sep-
2020 | Prior
to IA
DB
lock | Creation of
Amendment
version 1.1 | 
 
• Definition of enrolled set changed to show the actual scenario
 
• Formula of risk difference added
 
  | 
 
• Section 2.2
 
• Section 2.8.1
 
                     |
| 08-
Apr-
2021 | Post
IA
DB
lock     | Creation of
addendum
version 1.0  | 
 
• Changes of analysis in GI symptom ObsRO questionnaire based on data characteristics (data was not available prior to DBL and hence change has been done post DBL)
 
 | 
 
• Section 2.11
 
   |
| 08-
Apr-
2021 | Prior
DB
lock          | Creation of
amendment
1.2         | 
 
• Adding Serum ferritin TDT vs NTDT and baseline definition for lab assessemnts
 
• Adding figures related analysis in PRO section
 
                           | 
 
• Section 2.8.3
 
• Section 2.11
 
                    |

## List of abbreviations

|        |  |
|--------|--|
| AE     | Adverse event                                  |
| ATC    | Anatomical Therapeutic Classification          |
| CSR    | Clinical Study report                          |
| CTCAE  | Common Terminology Criteria for Adverse Events |
| DT     | Dispersible tablet                             |
| FAS    | Full Analysis Set                              |
| FCT    | Film-coated tablet                             |
| eCRF   | Electronic Case Report Form                    |
| MedDRA | Medical Dictionary for Drug Regulatory Affairs |
| NCI    | National Cancer Institute                      |
| NTDT   | Non-transfusion- dependent thalassemia         |
| PFS    | Progression-Free Survival                      |
| PK     | Pharmacokinetics                               |
| PPS    | Per-Protocol Set                               |
| PRO    | Patient-reported Outcomes                      |
| RAP    | Report and Analysis Process                    |
| SAP    | Statistical Analysis Plan                      |
| SOC    | System Organ Class                             |
| TDT    | Transfusion-dependent thalassemia              |
| TFLs   | Tables, Figures, Listings                      |
| WHO    | World Health Organization                      |

## 1 Introduction

This analysis plan module describes the statistical methods which will be used in the Phase II clinical study CICL670FIC05.

The main purpose of this document is to provide a summary of the statistical methodology that will be used for this clinical study; this includes a detailed description of data summaries. Analyses plan in this document refers to the related statistical analysis sections in the clinical study report.

The analysis described here will be conducted by Novartis using statistical software SAS® Version 9.4 according to the Statistical methods and data analysis Section 10 of the study protocol which will be available in Appendix 16.1.1 of the CSR. Important information will be given in the following sections and further details are provided, as applicable, in the Appendix 16.1.9 of the CSR.

Unless otherwise specified, the statistical methodologies including the analysis sets, analysis models, algorithms and conventions are following the Oncology study protocol CICL670FIC05 final version.

### 1.1 Study design

This is an open-label, multicenter, single arm study of deferasirox. This study aims to assess treatment patient preference for new deferasirox formulation (film-coated tablet) compared to reference deferasirox dispersible tablet formulation in transfusion-dependent thalassemia (TDT) and non-transfusion-dependent thalassemia (NTDT) patients throughout a 48 week treatment period.

Patients will undergo up to 4 weeks of screening period and if deemed eligible, will receive deferasirox dispersible tablet (DT) formulation for 24 weeks. After completion of 24 weeks patients will be transitioned on Week 25 to an equivalent dose of the deferasirox film coated tablet (FCT) formulation and continue treatment till Week 48. Completion of Week 48 indicates “End of Trial” of the Core Phase.

Patients can then continue deferasirox FCT formulation as per the judgment of the investigator, through an extension phase for maximum of 12 months counting from last dose of deferasirox FCT received at the end of period 2 on Core Phase.

#### Planned number of patients

It is intended that a total of 145 patients of age  $\geq 2$  years will be recruited in the study. Patients may have been previously treated with iron chelators (other than deferasirox DT) or be chelation-naïve.

[figure not shown]
The overall study design is as follows:

- **Core phase:**
  - Screening phase which lasts for maximum 4 weeks to determine whether the patient is eligible or not and is followed by
  - Baseline visit (Day 1)

- Period 1: deferasirox DT as 10-40 mg/kg/day dose regimen of dispersible tablet formulation for 24 weeks followed by
  - Period 2: deferasirox FCT as 7-28 mg/ kg/ day dose regimen of film coated tablet for 24 weeks.
- **Extension Phase:**
    - Deferasirox FCT as 7-28 mg/kg/ day dose regimen of film-coated tablet.

The overall study design is given in the following figure:

**Figure 1-1 Study Design**

Patients who discontinue study treatment before completing the study should be scheduled for a visit as soon as possible, at which time all of the assessments listed for SEC must be performed.

**Primary analysis time point**

The primary analysis will be performed at Week 48 to evaluate patient preference of deferasirox DT vs. deferasirox FCT formulations.

**Interim analysis**

The interim analysis will be performed at Week 48 to assess the patient preference after 6 months with deferasirox FCT treatment in comparison to deferasirox DT.

**1.2 Study objectives and endpoints**

The objective of the study is to assess patient preference of deferasirox DT or deferasirox FCT in thalassemia patient.

**Table 1.2.1: Study objectives and related endpoints**

| Objective   | Endpoint  |
|---|---|
| Primary  |   |
| To evaluate patient preference between deferasirox FCT and deferasirox DT | Proportion of patients claimed preference of deferasirox FCT over deferasirox DT as measured by preference questionnaire at Week 48 |

| Objective   | Endpoint   |
|---|--|
| Secondary  |  |
| To evaluate patient preference of deferasirox FCT or deferasirox DT or previous iron chelation                                      | Proportion of patients claimed preference of deferasirox FCT, deferasirox DT, and previous iron chelation as measured by preference questionnaire at Week 28   |
| To evaluate patient preference of deferasirox DT or previous iron chelation   | Proportion of patients claimed preference of deferasirox DT, over previous iron chelation as measured by preference questionnaire at Week 4 and Week 24  |
| To evaluate the reason behind preference for deferasirox FCT or deferasirox DT  | Proportion of preference reasons for deferasirox FCT over deferasirox DT as measured by preference questionnaire at Week 28 and Week 48  |
| To evaluate the effect of deferasirox FCT compared with deferasirox DT on patient compliance using pill count                       | Relative consumed pill count during deferasirox FCT (Week 25 to 48) compared with deferasirox DT (Baseline day 1 to Week 24)   |
| To evaluate the effect of deferasirox FCT compared with deferasirox DT or previous iron chelation on patient palatability using PRO | Absolute and relative change in domain scores of palatability questionnaire over time during deferasirox FCT (Week 28 to 48) compared with deferasirox DT (Week 4 to 24) or previous iron chelation (Screening)      |
| To evaluate the effect of deferasirox FCT compared with deferasirox DT or previous iron chelation on patient satisfaction using PRO | Absolute and relative change in domain scores of SICT questionnaire over time during deferasirox FCT (Week 28 to 48) compared with deferasirox DT (Week 4 to 24) or previous iron chelation (Screening)              |
| To evaluate the effect of deferasirox FCT compared with deferasirox DT or previous iron chelation on patient GI symptom using PRO   | Absolute and relative change in domain scores of SICT questionnaire over time during deferasirox FCT (Week 28 to 48) compared with deferasirox DT (Week 4 to 24) or previous iron chelation (Screening)              |
| To evaluate the overall safety of deferasirox FCT compared with deferasirox DT  | Overall safety, as measured by frequency and severity of adverse events and changes in laboratory values of interest during deferasirox FCT (Week 25 to 48) compared with deferasirox DT (Baseline day 1 to Week 24) |
| To evaluate efficacy of deferasirox ( both DT and FCT) in decreasing serum ferritin levels  | Absolute and relative change from baseline ( Day 1) in serum ferritin on monthly basis   |

## 2 Statistical methods

### 2.1 Data analysis general information

All analysis will be performed by NBS CONEXTS, Novartis.

It is planned that the data from all centers that participate in this study will be used for analysis. Analysis datasets and statistical outputs will be produced using the most recent SAS® Version 9.4 (SAS Institute Inc., Cary, NC, USA), and stored in Novartis global programming & statistical environment (GPS).

As the primary endpoint analysis will be performed at Week 48, there will be a database lock after all patients have completed Week 48 assessments. The proposed statistical analysis for interim analysis is described in [Section 2.14](#). A final database lock will occur when all patients have completed the study.

All summary statistics for continuous variables will include n (number), mean, standard deviation (SD), median, lower and upper quartiles (Q1, Q3), minimum, maximum, and, where applicable, the estimate and the 95% confidence intervals (CI) of mean. For categorical variables, descriptive statistics will include the number (frequencies) and percentage of patients in each category. Summary statistics will also be presented graphically wherever applicable.

If not otherwise specified, p-values and CI will be presented as two-sided. Unless otherwise stated, the default level of significance will be set to 5% (two-sided, family-wise type-I-error).

All data analysis will be presented by treatment group, i.e. DFX DT and DFX FCT, iron chelation status (naïve or pre-treated) and by thalassemia transfusion status (TDT or NTDT), wherever applicable. Efficacy and safety data for the core and extension phases will also be presented by the above groups. Since this study also includes pediatric patients, all key safety and efficacy endpoints will also be summarized by the age groups as defined in the protocol and [Section 2.2.1](#).

The analysis will be conducted on all patients' data at the specific time-points (Week 4, 24, 28, and 48), wherever applicable and at the time the study (both core and extension phases) ends.

Unless otherwise specified, if there are additional data available for any assessment (for example data on unscheduled visit) then the average of the available values will be presented under the dedicated visit.

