## 2.8.3 Laboratory data

The summary of laboratory evaluations will be presented for different groups of laboratory tests (hematology, serum chemistry, serum ferritin, serum creatinine, and urinalysis) for different treatment periods (core and extension). Descriptive summary statistics for the change from baseline to each study visit will be presented. These descriptive summaries will be presented by test group, laboratory test and treatment group. Change from baseline will be summarized only for the patients who have both baseline and post-baseline assessment. For each parameter, maximum change from baseline within each study period will be evaluated analogously.

In addition, shift tables will be provided for all parameters to compare a patient's baseline laboratory evaluation relative to the visit's observed value. For the shift tables, the normal laboratory ranges will be used to evaluate whether a particular laboratory test value was normal, low, or high for each visit value relative to whether or not the baseline value was normal, low, or high. These summaries will be presented by laboratory test and treatment group. Shifts will be presented by visit as well as for most extreme values post-baseline.

Grading of laboratory values will be assigned programmatically as per NCI Common Terminology Criteria for Adverse Events (CTCAE). The calculation of CTCAE grades will be based on the observed laboratory values only, clinical assessments will not be taken into account.

CTCAE Grade 0 will be assigned for all non-missing values not graded as 1 or higher. Grade 5 will not be used.

For laboratory tests where grades are not defined by CTCAE, results will be categorized as low/normal/high based on laboratory normal ranges.

The following summaries will be generated separately for hematology and biochemistry tests:

- Reporting of all laboratory data with values flagged to show the corresponding CTCAE grades if applicable and the classifications relative to the laboratory normal ranges ([Table 5.3.1](#))

For laboratory tests where grades are defined by CTCAE

- Worst post-baseline CTCAE grade (regardless of the baseline status). Each patient will be counted only once for the worst grade observed post-baseline.
- Shift tables using CTCAE v4.3 grades to compare baseline to the worst on-treatment value

For laboratory tests where grades are not defined by CTCAE

- Shift tables using the low/normal/high/ (low and high)

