## 5.3 Laboratory parameters derivations

**Table 5.3.1 Definition of notable/extended ranges for laboratory test**

| Laboratory test                          | Criteria for notable ranges  |
|--|--|
| Platelet count                           | < 100 x 10  /L (extended range <50×10  /L)   |
| Absolute neutrophils                     | < 1.5 x 10  /L (extended range <0.5×10  /L)  |
| Serum creatinine                         | > 33% increase from baseline and > ULN at two consecutive measurements at least 7 days apart   |
| Creatinine clearance*                    | <60 mL/min at two consecutive measurements at least 7 days apart (extended range <40 mL/min at two consecutive measurements at least 7 days apart) |
| Urinary protein/urinary creatinine ratio | ≥ 1.0 (mg/mg) at two consecutive measurements at least 7 days apart  |
| ALT and AST                              | >5 x ULN and >2 x baseline value (extended range >10×ULN and >2×baseline value)  |

\* Creatinine clearance will be estimated using the Schwartz formula

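### SAP 2.1 averages scheduled and unscheduled values under one visit with no exemption for safety data, so by-visit laboratory and vital-sign outputs can hide abnormal results, and the SAP does not say that worst-value and confirmed-abnormality derivations use the raw values.

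*SAP*

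**What the plan says.** SAP 2.1 (Data analysis general information) sets a default for repeat data, giving unscheduled visits as its example: "then the average of the available values will be presented under the dedicated visit". It covers every assessment and gives way only where something else is specified.

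SAP 2.8.3 (Laboratory data) plans summaries of change from baseline at each visit, maximum change within each study period, worst post-baseline CTCAE grade and shift tables. On shifts it says "Shifts will be presented by visit as well as for most extreme values post-baseline". On grading it says "The calculation of CTCAE grades will be based on the observed laboratory values only, clinical assessments will not be taken into account". SAP 2.8.4.2 (Vital signs) summarises change from baseline by scheduled visit. None of these sections says how unscheduled or repeat values are used.

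Table 5.3.1 defines notable ranges. Three of its six rows need confirmation:
- for serum creatinine the rule is "> 33% increase from baseline and > ULN at two consecutive measurements at least 7 days apart"
- the rows for creatinine clearance and the urinary protein/creatinine ratio set the same demand of a second result a week or more later, at below 60 mL/min (with a stricter extended range) and at 1.0 mg/mg or above

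The rows for platelets, neutrophils and ALT/AST need one value only. SAP 2.8 also states that all data are listed.

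**The concern.** A safety repeat is often a response to an abnormal result. If the two results are averaged, the visit shows a value that was never measured and that lies closer to normal than the worse of the two. In a by-visit table this hides the abnormality or reduces its size. If the same visit-level value feeds the worst-case outputs, the peak is lost there too. A criterion that needs two separate measurements cannot be met by the single number they have been merged into.

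Changes in laboratory values of interest under FCT compared with DT are part of a stated secondary safety endpoint (SAP Table 1.2.1). A default that can understate renal or hepatic abnormalities therefore bears on an objective of the trial. The primary preference comparison is not at issue.

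**Working it through.** The plan gives no figure to reproduce here. The check applies the averaging rule to the plan's own thresholds and visit windows. All laboratory values below are illustrations, not taken from the documents.

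**1. By-visit outputs.** The by-visit shift tables classify values as low, normal or high. Take one scheduled and one unscheduled ALT, *a* and *b*, in multiples of ULN. The visit shows (*a* + *b*)/2, which is no longer above ULN whenever *a* + *b* ≤ 2. A modest elevation can thus disappear from a by-visit shift table. A larger one stays high but shrinks: (6 + 2)/2 = 4 x ULN.

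**2. Single-value criteria, if built on averages.** Inputs are the Table 5.3.1 thresholds, with the ALT condition of more than 2 x baseline assumed met.
- ALT 6 and 2 x ULN: average 4, so the > 5 x ULN flag is lost.
- Scheduled ALT of 1 x ULN: the average exceeds 5 only if the unscheduled value exceeds 2 × 5 − 1 = 9 x ULN, and exceeds 10 only if it exceeds 2 × 10 − 1 = 19 x ULN.
- Platelets 40 and 120 x 10⁹/L: average 80. The extended flag (< 50) is lost and the notable flag (< 100) stays.

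**3. Confirmed criteria, if built on averages.** Assume creatinine baseline 0.80 and ULN 1.0. The value must exceed 1.33 × 0.80 = 1.064, which is also above ULN. Results of 1.15 and 1.12 ten days apart give 1.15/0.80 = 1.44 and 1.12/0.80 = 1.40, that is +44% and +40%, so the criterion is met. Averaged, one value remains, (1.15 + 1.12)/2 = 1.135, and it cannot confirm itself.

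**4. Can two such results fall under one visit?** The SAP does not say how an unscheduled value is assigned to a visit. Suppose the SAP 2.1.1 visit windows are used.
- Visits 3 to 7: ±2 days, a span of 4 days. Two results at least 7 days apart cannot share a window.
- Visits 8 to 26 and 777: ±7 days, a span of 14 days. They can.
- The ten-day example fits the Visit 8 window (days 133 to 147) only if the scheduled visit is at least 3 days early: 137 + 10 = 147. A repeat on day 150 after an on-target day 140 lies outside it.
- In the core phase the windows cover 5 × 5 + 8 × 15 = 145 of the 332 days from day 12 to day 343. An unscheduled value on any other day has no defined visit.

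**5. Can the criteria still be met without unscheduled data?** Yes. Scheduled visits from Visit 3 on are nominally 14 or 28 days apart, so two consecutive scheduled results satisfy the 7-day gap and are not averaged with each other.

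**The case against.** The strongest reply is that the rule concerns what is shown under a visit and yields where something else is specified. Worst grade, most-extreme shift and maximum change within a period are not by-visit outputs, and an average is neither an observed nor an extreme value. The Table 5.3.1 criteria are written on measurements separated in time, which makes sense only for individual dated results. This stands as a reasonable reading. It is not the only one: in SAP 2.8.3 the restriction to observed values is contrasted with clinical assessments, not with averages, and the same section speaks of one observed value per visit.

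Three stronger conclusions might be inferred, and the documents do not support them:
- **That the SAP prescribes merging, so confirmed abnormalities are lost.** It does not. Merging is a possible result of an unclear rule.
- **That counts of notable values will be understated.** SAP 2.8.3 cites Table 5.3.1 only for flagging reported laboratory data, and Protocol 10.5.3.3 calls that output a listing. Neither section describes a table of counts.
- **That repeats are usually unscheduled.** Protocol 6.2.1.2 names the next visit first for a creatinine rise and otherwise leaves timing to clinical indication. Protocol 6.2.1.4 names the next visit for proteinuria. Repeats can be unscheduled, and no more can be said.

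It is also fair that laboratory abnormalities judged clinically significant, or requiring a treatment change, are recorded as adverse events (Protocol 8.1.1 and 8.1.2), which gives them a separate route into the safety tables. This softens the consequence but does not correct the laboratory tables. Finally, using only the scheduled value removes an unscheduled peak from by-visit tables altogether. That is a real but small cost, provided the worst-value outputs use every measurement.

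**Conclusion.** The point holds for by-visit laboratory and vital-sign summaries and by-visit shift tables: as written, these would show averages that can hide or shrink an abnormal result. For worst grade, most-extreme shift, maximum change and Table 5.3.1 flags it holds as an ambiguity. They can be read as using raw values, the SAP does not say so, and dilution or merging follows only if they are built on visit averages. Merging affects the three confirmed renal criteria and, if the visit windows govern assignment, arises only from Visit 8 onward.

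The size of the effect on the trial's tables cannot be estimated, because the documents give no rate of unscheduled testing. The examples show what the rule can do to one patient's values, not how often it would. The change is worth making because the default is explicit, serves no evident purpose for safety data and is easy to remove.

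**What to change.** In SAP 2.1 and 2.8.3:
1. Exclude safety data from the averaging default. The mean of three seated blood pressure readings at a visit (Protocol 7.2.2.2) is a measurement procedure and can stay.
2. For by-visit summaries and shifts, use the scheduled value or, failing that, the one closest to the target day.
3. State that worst CTCAE grade, most-extreme shift, maximum change and Table 5.3.1 flags use every individual scheduled and unscheduled measurement with its actual date.
4. Define how unscheduled values are assigned to visits, including those outside every window.

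The cost is a few sentences and a standard derivation change, with no new data. The SAP's document history places its latest changes after the interim database lock, so any core-phase tables already produced with averages would need to be rerun. An unscheduled peak will no longer appear in by-visit tables, but it is captured in the worst-value outputs and listings.
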